1 INTERIM SAP SYNOPSIS

TITLE OF STUDY: A Phase 3 Open-Label, Single-Arm Study To Evaluate The Efficacy and Safety of BMN 270, an Adeno-Associated Virus Vector–Mediated Gene Transfer of Human Factor VIII at a dose of 4E13 vg/kg in Hemophilia A Patients with Residual FVIII Levels \leq 1 IU/dL Receiving Prophylactic FVIII Infusions

PROTOCOL NUMBER: 270-302

STUDY OBJECTIVES, DESIGN, DATA ACCESS PLAN, AND INTERIM ANALYSIS

The objectives of the study are to assess the efficacy of BMN 270 on FVIII activity, usage of exogenous FVIII replacement therapy, and number of bleeding episodes; patient-reported outcomes (PROs); and to evaluate the long-term safety of BMN 270 following intravenous infusion.

This is a Phase 3, single-arm, open-label study in hemophilia A (HA) patients with residual FVIII levels \leq 1 IU/dL treated continuously with prophylactic exogenous FVIII for a minimum of one year prior to enrollment. It was planned that subjects would be enrolled at approximately 40 sites worldwide. Approximately 40 adult subjects with severe HA were planned to receive a 4E13 vg/kg dose of BMN 270 as a single intravenous infusion:

- Directly enrolled subjects: The first approximately 5 subjects will enroll in the study with at least 12 months of well-documented high-quality historical data concerning previous bleeding episodes and exogenous FVIII usage.
- Study 270-902 rollover subjects: The rest, approximately 35 subjects, will enroll in the study after having completed approximately 6 months’ participation in the BioMarin-sponsored non-interventional study 270-902, in which bleeding and FVIII use data prior to gene therapy will be prospectively collected.

In order to minimize bias and to preserve the scientific and business integrity of the single-arm and open-label study, a data access plan (DAP) was implemented. This document provided guidelines for accessing post-treatment study data and applies to study team members, including personnel from within BioMarin, from external vendors and service providers, from the Data Monitoring Committee (DMC), and from study sites. Role-based access control to study data, both individual patient-level data values as well as aggregated summaries of longitudinal data in an individual patient or across multiple patients, was implemented to minimize potential bias and achieve appropriately controlled decision-making, while preserving operational efficiency. It was enforced by the DAP that individuals who had knowledge of the key efficacy variables (FVIII activity, FVIII usage, and bleeding counts) did not make or influence decisions that would alter the study design or conduct, or the collection or analysis of the key efficacy variables so as to bias the studies’ key efficacy results. The data access control has been lifted from Study 270-302 since September 2019 because only one subject was enrolled in the study and enrollment has been terminated.

In addition, an independent DMC, consisting of experts in clinical trials, statistics, and hemophilia, has been convened in order to assure safe and ethical conduct of the clinical trial. The DMC, supported by an independent statistical service provider, have access to all available data, including both safety and efficacy (e.g., FVIII activity), during the study on an ongoing basis.

An interim analysis was planned after the first approximately 20 HIV-negative subjects have completed the Week 26 visit (or have discontinued study participation prior to Week 26). The concept of the interim analysis was to facilitate initiation of regulatory review of the ongoing study in the event that robust improvements (essentially normalization) in Factor VIII activity in a sufficient proportion

of the population are observed. The interim analysis will not be implemented since enrollment of the study has been terminated since only one subject was enrolled

In order to support a filing of application for marketing approval of BMN 270 based on Study 270-301 interim data, an additional interim analysis of Study 270-302, which was covered in interim analysis plan version 1 (dated 24 April 2019), was implemented around the same time of the Study 270-301 interim analysis to provide supportive baseline and safety data.

In order to provide ancillary baseline, efficacy and safety data to support filing of application for marketing approval of BMN 270 based on Study 270-301 Year 1 data, a second interim analysis is planned; this analysis plan is for this second interim analysis. Additional interim analyses of Study 270-302 may also be performed depending on the amount of additional data accumulated when necessary

INTERIM ANALYSIS POPULATIONS

As mentioned above, in order to support a filing of application for marketing approval of BMN 270 based on Study 270-301 Year 1 data, an interim analysis of Study 270-302 is planned to provide supportive baseline, efficacy and safety data. The following are populations for this interim analysis.

All Screened Subjects: all screened subjects in the study.

All Enrolled Subjects: all enrolled subjects in the study.

Intention-to-treat (ITT) Population: all enrolled, treated subjects in the study.

Screening status and screen failure reasons will be listed for all screened subjects. [REDACTED]

ENDPOINTS AND ANALYSES:

Primary and secondary efficacy endpoints and analyses:

Since only one subject was enrolled in the study, no summary tables will be generated and only [REDACTED]

Safety endpoints and analyses:

 19.2 Preferred Terms Suggestive of Thromboembolic Events32

3 LIST OF ABBREVIATIONS

Abbreviation	Definition
AAV	Adeno-associated virus
ABR	Annualized bleeding rate
ADR	Adverse drug reaction
AE	Adverse event
ALP	Alkaline phosphatase
ALT	Alanine transaminase
AST	Aspartate transaminase
BU	Bethesda Unit
CRF	Case report form
CTCAE	Common Terminology Criteria for Adverse Events
CTL	Cytotoxic T lymphocytes
DAP	Data access plan
DILI	Drug-Induced Liver Injury
DMC	Data Monitoring Committee
ECG	Electrocardiogram
eCRF	Electronic case report form
EOSI	Events of special interest
ETV	Early termination visit
FVIII	Coagulation factor VIII
HA	Hemophilia A
hFVIII	Human coagulation factor VIII
HLT	High Level Term
ICH	International Conference on Harmonisation
IV	Intravenous
LDH	Lactate dehydrogenase
LLOQ	Lower limit of quantitation
MedDRA	Medical Dictionary for Regulatory Activities
NAb	Neutralizing antibody
PBMC	Peripheral blood mononuclear cells
PRO	Patient reported outcome
QoL	Quality of life
rhFVIII	Recombinant human FVIII protein
SAE	Serious adverse event
SAP	Statistical analysis plan

SFU	Spot-forming units
TAb	Total antibody
TEAE	Treatment-emergent adverse event
TI	Transduction Inhibition
ULN	Upper limit of normal
Vg/kg	Vector genomes per kilogram
WHO	World Health Organization

4 INTRODUCTION

This document describes the statistical methods to be implemented in the interim analysis of data collected under clinical study protocol 270-302, “A Phase 3 Open-Label, Single-Arm Study To Evaluate The Efficacy and Safety of BMN 270, an Adeno-Associated Virus Vector–Mediated Gene Transfer of Human Factor VIII at a dose of 4E13 vg/kg in Hemophilia A Patients with Residual FVIII Levels \leq 1 IU/dL Receiving Prophylactic FVIII Infusions” (Global Amendment 4, 09 November 2018). The Interim SAP contains definitions of analysis populations, derived variables, and statistical methods for the analyses of baseline, efficacy and safety data in order to support a filing of application for marketing approval of BMN 270 based on Study 270-301 Year 1 data.

The objectives of the study are to assess the efficacy of BMN 270 on FVIII activity, usage of exogenous FVIII replacement therapy, and number of bleeding episodes; patient-reported outcomes (PROs); and to evaluate the long-term safety of BMN 270 following intravenous infusion.

This is a Phase 3, single-arm, open-label study in hemophilia A (HA) patients with residual FVIII levels \leq 1 IU/dL treated continuously with prophylactic exogenous FVIII for a minimum of one year prior to enrollment. It was planned that subjects would be enrolled at approximately 40 sites worldwide. Approximately 40 adult subjects with severe HA were planned to receive a 4E13 vg/kg dose of BMN 270 as a single intravenous infusion:

- Directly enrolled subjects: The first approximately 5 subjects will enroll in the study with at least 12 months of well-documented high-quality historical data concerning previous bleeding episodes and exogenous FVIII usage.
- Study 270-902 rollover subjects: The rest, approximately 35 subjects, will enroll in the study after having completed approximately 6 months’ participation in the BioMarin-sponsored non-interventional study 270-902, in which bleeding and FVIII use data prior to gene therapy will be prospectively collected.

In order to minimize bias and to preserve the scientific and business integrity of the single-arm and open-label study, a data access plan (DAP) was implemented. This document provided guidelines for accessing post-treatment study data and applies to study team members, including personnel from within BioMarin, from external vendors and service providers, from the Data Monitoring Committee (DMC), and from study sites. Role-based access control to study data, both individual patient-level data values as well as aggregated summaries of longitudinal data in an individual patient or across multiple patients, was implemented to minimize potential bias and achieve appropriately controlled decision-making, while preserving operational efficiency. It was enforced by the DAP that individuals

who had knowledge of the key efficacy variables (FVIII activity, FVIII usage, and bleeding counts) did not make or influence decisions that would alter the study design or conduct, or the collection or analysis of the key efficacy variables so as to bias the study's key efficacy results. The data access control has been lifted from Study 270-302 since September 2019 because only one subject was enrolled in the study and enrollment has been terminated.

In addition, an independent DMC, consisting of experts in clinical trials, statistics, and hemophilia, has been convened in order to assure safe and ethical conduct of the clinical trial. The DMC, supported by an independent statistical service provider, have access to all available data, including both safety and efficacy (e.g., FVIII activity), during the study on an ongoing basis.

An interim analysis was planned after the first approximately 20 HIV-negative subjects have completed the Week 26 visit (or have discontinued study participation prior to Week 26). The concept of the interim analysis was to facilitate initiation of regulatory review of the ongoing study in the event that robust improvements (essentially normalization) in Factor VIII activity in a sufficient proportion of the population are observed. This interim analysis will not be implemented since enrollment of the study has been terminated since only one subject was enrolled.

In order to support a filing of application for marketing approval of BMN 270 based on Study 270-301 interim data, an additional interim analysis of Study 270-302 was implemented around the same time of the Study 270-301 interim analysis to provide supportive baseline and safety data.

In order to provide ancillary baseline, efficacy and safety data to support filing of application for marketing approval of BMN 270 based on Study 270-301 Year 1 data, a second interim analysis is planned; this analysis plan is for this additional interim analysis. Additional interim analyses of Study 270-302 may also be performed depending on the amount of additional data accumulated when necessary.

5 GENERAL ANALYSIS CONSIDERATIONS

Since only one subject was enrolled in the study, [REDACTED]

5.1 Interim Analysis Populations

As mentioned above, in order to support a filing of application for marketing approval of BMN 270 based on Study 270-301 interim Year 1 data, an interim analysis of Study 270-302 is planned to provide supportive baseline, efficacy and safety data. The following are populations for this interim analysis.

All Screened Subjects: all screened subjects in the study.

All Enrolled Subjects: all enrolled subjects in the study.

Intention-to-treat (ITT) Population: all enrolled, treated subjects.

Screening status and screen failure reasons will be listed for all screened subjects.

Disposition data will be listed for all enrolled subjects. [REDACTED]

5.2 Treatment Group Presentation

Only listings will be provided since only one subject was enrolled.

5.3 Study Day Derivation

Study day is assigned as follows:

- The investigational product infusion date is designated as Day 1.
- For visit days after infusion, study day = visit date – Day 1 date + 1.
- For visit days prior to infusion, study day = visit date – Day 1 date (Thus, study days for screening visits are negative numbers.)

5.4 Visit Windows for Analysis

All data will be summarized by week, wherever applicable. An assessment for a subject will be classified according to the study day of the assessment where it falls within a given window (see Appendix Section 19.1).

For safety endpoints, such as liver tests and vital signs, windows are designated for each scheduled week of visit and centered on a target day; for example, the target day for a Week 4 visit is Study Day 29. If there are two or more assessments within a designated window, the assessment that is closest to the target day will be used for analyses. If the two

closest assessments to the target day are equidistant from the target day, then the mean of the two assessments will be used for analyses unless otherwise specified.

Appendix (Section 19.1) lists the weeks assigned for the analyses of the clinical endpoint assessments and the corresponding range of treatment days (window) during which a visit may have occurred by analysis parameter.

5.5 Baseline Value

The baseline values are calculated using data during the one year prior to enrollment for the following parameters:

- annualized utilization of exogenous FVIII replacement therapy
- annualized number of treated bleeding episodes
- baseline ABR for treated bleeds
- baseline ABR for all bleeds

The baseline values of other assessments are defined as the last available measurement prior to the administration of investigational product.

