b Includes baseline FVIII activity (chromogenic substrate FVIII assay and one-stage clotting FVIII assay), coagulation exploratory assay, hFVIII inhibitor level (Bethesda assay with Nijmegen modification), hFVIII total antibody titer, and hFVIII protein assay. Baseline activity should be assessed at trough (at least >72 hours after last dose of replacement FVIII therapy, or 5x the known half-life of the FVIII concentrates administered).

c Sample collection on the day of the infusion visit must be performed before the BMN 270 infusion is given. Screening, Smart Re-screening, and Infusion Day samples will be tested in an AAV5 TAb pre-screening assay specifically developed for enrollment purposes. Baseline and all post-dose samples will be tested in a different AAV5 TAb post-dose immunogenicity monitoring assay

d Patients with documented negative results within the last 30 days do not need to be retested. Hepatitis B screening should include hepatitis B surface antigen (HBsAg), hepatitis B surface antibody (HBsAb), and hepatitis B core antibody (HBcAb).

e Refer to [Table 9.7.8.2.1](#) for laboratory assessments to be included, and to [Table 9.7.8.3.1](#) for liver tests. ABO blood typing assessment should be performed as part of the hematology assessment (at Baseline, or at another regularly scheduled visit prior to the end of the subject's participation in the study).

f Includes HLA genotyping and FVIII genotyping.

g Blood samples will be collected from subjects to evaluate biochemical, molecular, cellular, and genetic/genomic aspects relevant to hemophilia A, coagulation, and/or AAV gene transfer, and to develop assays used for these evaluations. Subjects may choose to opt out of the exploratory genetic/genomic research being done to study or try to discover genes that are not yet known to be associated with hemophilia A. While exploratory samples will be collected at the time points indicated above, testing of these samples (including those for TGA assay, and any other exploratory assessments) will be performed only as deemed necessary by the Sponsor.

h Should the screening visit occur within 30 days of the drug infusion, physical examination, blood chemistry, LTs, hematology, urine tests, and coagulation tests do not need to be repeated at Baseline.

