### **12.3 Baseline Visit**

Baseline values will be recorded from 1 to 7 days prior to the treatment visit. The following procedures will be performed during the Baseline Period:

- Brief physical examination
- Vital signs
- Assessment of Adverse Events and Concomitant Medications
- Documentation of bleeding episodes and FVIII usage (by either subject or clinical information)
- Blood sample for AAV5 TI assay
- Blood sample for AAV5 TAb assay
- Blood chemistry, hematology, and coagulation tests (refer to [Table 9.7.8.2.1](#))
  - ABO blood typing assessment should be performed as part of the hematology assessment (at Baseline, or at another regularly scheduled visit prior to the end of the subject's participation in the study).
- Urine Tests (refer to [Table 9.7.8.2.1](#))
- Liver Tests (refer to [Table 9.7.8.3.1](#))
- Samples for hFVIII Assays
  - Baseline FVIII activity – chromogenic substrate FVIII assay
  - Baseline FVIII activity level – one-stage clotting FVIII assay
  - hFVIII coagulation activity exploratory assay
  - hFVIII inhibitors (Bethesda assay with Nijmegen modification)
  - hFVIII total antibody assay
  - hFVIII protein assay
- PBMC collection for CTL baseline
- Von Willebrand Factor Antigen (VWF:Ag)
- TGA Assay
- PCR of vector DNA in blood, saliva, urine, semen, and stools
- Exploratory biomarker assessments

[figure not shown]
- Haemo-QoL-A assessment
- EQ-5D-5L
- Hemophilia Activities List (HAL)
- Work Productivity and Activity Impairment plus Classroom Impairment Questions: Hemophilia Specific (WPAI+CIQ:HS) questionnaire
- Patient Reported Outcomes, Burdens, and Experiences (PROBE) questionnaire

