#### **12.4 Treatment Visit/BMN 270 Infusion Visit (Day 1)**

There will be one treatment visit for each subject. Subjects will remain in the clinic for at least 8 hours for the BMN 270 Infusion Visit. The following procedures will be performed during the BMN 270 Infusion Visit:

- Brief physical examination
- Assessment of Adverse Events and Concomitant Medications
- AAV5 TAB Assay (sample collected pre-infusion for analysis)
- Fasting lipid panel (blood triglycerides, total cholesterol, HDL cholesterol, and LDL cholesterol) (sample collected pre-infusion)
  - Subjects will fast for at least 8 hours prior to pre-infusion laboratory sampling on the day of the infusion visit.
- Exploratory biomarker assessments
- BMN 270 Infusion
- Vital Signs
  - Vital signs will be recorded prior to BMN 270 infusion and then every 15 minutes ( $\pm$  5 minutes) during BMN 270 infusion. Following infusion, vital signs will be monitored every 1 hour ( $\pm$  5 minutes) for at least 8 hours during the subject's stay in the clinic.
- PCR of vector DNA in blood, saliva, urine, semen, and stools
  - Collection of samples for PCR testing should occur between 2 and 24 hours after the BMN 270 infusion has been completed

In case of hypersensitivity or adverse drug reaction, safety assessment, including physical examination and vital signs, will be done and additional blood samples will be collected

In-patient observation can be extended and additional blood samples can be collected if deemed necessary at the discretion of the Investigator and Medical Monitor.

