15 IMMUNOGENICITY ASSESSMENT

Assays to detect pre-existing immunogenicity specific for AAV5, including plasma derived inhibitors of transduction (transduction inhibition or TI) and total antibody (TAb) assays, will be tested at the Screening visit before BMN 270 infusion is given and at post-baseline visits according to the protocol's schedule of events. [REDACTED]

Two assays are in place to determine immunogenicity to the human FVIII transgene product. The first is a total antibody (TAb) assay to detect binding antibodies in patient plasma directed against human FVIII and is reported as negative or positive with titer. The second is to evaluate neutralizing antibodies (Nab) capable of interfering with FVIII activity (FVIII Inhibitors) and is determined using the Bethesda assay with Nijmegen modification. This assay is reported out in Bethesda Units (BU), with a value of <0.6 considered negative. Both assays will be performed on patient plasma samples obtained at the screening visit, and at post-baseline visits according to the protocol's schedule of events. [REDACTED]

Cellular immunity in the form of cytotoxic T lymphocytes (CTL) will be evaluated by Interferon-gamma (IFN- γ) ELISpot assay of peripheral blood mononuclear cells (PBMC). PBMC will be stimulated with overlapping peptide pools derived from the AAV5 capsid protein or human FVIII protein sequences to evaluate IFN- γ secretion by CTL targeting both the AAV5 capsid and the FVIII transgene product. Cellular immunity will be evaluated at baseline and at post-infusion visits according to the protocol's schedule of events and is reported as positive or negative by peptide pool stimulation based on the number of spot forming units (SFU) per 10^6 PBMC. A data listing will be generated reporting the number of SFU 10^6 PBMC for each peptide pool and control (positive and negative) stimulation for each patient at each study visit tested. In addition, immunogenicity and alanine transaminase data will be plotted over time and overlaid in the figure.

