19 APPENDICES
19.1 Visit Windows

Assessment	Derived Visit	Scheduled Visit Day^a	Window^b
Liver tests, Vital signs, and other central lab tests	Baseline ^c	Day -1	≤ Day 1
	Week 1	Day 8	Days [2, 11]
	Week 2	Day 15	Days [12, 18]
	Week 3	Day 22	Days [19, 25]
	Week 4	Day 29	Days [26, 32]
	Week 5	Day 36	Days [33, 39]
	Week 6	Day 43	Days [40, 46]
	Week 7	Day 50	Days [47, 53]
	Week 8	Day 57	Days [54, 60]
	Week 9	Day 64	Days [61, 67]
	Week 10	Day 71	Days [68, 74]
	Week 11	Day 78	Days [75, 81]
	Week 12	Day 85	Days [82, 88]
	Week 13	Day 92	Days [89, 95]
	Week 14	Day 99	Days [96, 102]
	Week 15	Day 106	Days [103, 109]
	Week 16	Day 113	Days [110, 116]
	Week 17	Day 120	Days [117, 123]
	Week 18	Day 127	Days [124, 130]
	Week 19	Day 134	Days [131, 137]
	Week 20	Day 141	Days [138, 144]
	Week 21	Day 148	Days [145, 151]
	Week 22	Day 155	Days [152, 158]
	Week 23	Day 162	Days [159, 165]
	Week 24	Day 169	Days [166, 172]
Week 25	Day 176	Days [173, 179]	
Week 26	Day 183	Days [180, 186]	
Week 27	Day 190	Days [187, 193]	
Week 28	Day 197	Days [194, 200]	
Week 29	Day 204	Days [201, 207]	
Week 30	Day 211	Days [208, 214]	
Week 31	Day 218	Days [215, 221]	
Week 32	Day 225	Days [222, 228]	
Week 33	Day 232	Days [229, 235]	
Week 34	Day 239	Days [236, 242]	
Week 35	Day 246	Days [243, 249]	
Week 36	Day 253	Days [250, 259]	
Week 38	Day 267	Days [260, 273]	
Week 40	Day 281	Days [274, 287]	

Assessment	Derived Visit	Scheduled Visit Day^a	Window^b
	Week 42	Day 295	Days [288, 301]
	Week 44	Day 309	Days [302, 315]
	Week 46	Day 323	Days [316, 329]
	Week 48	Day 337	Days [330, 343]
	Week 50	Day 351	Days [344, 357]
	Week 52	Day 365	Days [358, 371]
	Week 56	Day 393	Days [372, 406]
	Week 60	Day 421	Days [407, 434]
	Week 64	Day 449	Days [435, 462]
	Week 68	Day 477	Days [463, 490]
	Week 72	Day 505	Days [491, 518]
	Week 76	Day 533	Days [519, 546]
	Week 80	Day 561	Days [547, 574]
	Week 84	Day 589	Days [575, 602]
	Week 88	Day 617	Days [603, 630]
	Week 92	Day 645	Days [631, 658]
	Week 96	Day 673	Days [659, 686]
	Week 100	Day 701	Days [687, 714]
	Week 104	Day 729	Days [715, 742]

^a Relative to the BMN 270 infusion day (Day 1)

^b Visit day is calculated as (visit date – date of infusion date + 1) if post infusion and (visit date – date of infusion date) if before infusion

^c Baseline visit value is defined as the last available measurement prior to BMN 270 dosing.

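### Does the SAP's last-pre-dose rule give AAV5 total antibody a baseline from a different assay than its post-dose results?

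*SAP*

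**What the plan says.** SAP Section 5.5 gives a one-year look-back baseline to FVIII use and bleeding, and one general rule to everything else: "The baseline values of other assessments are defined as the last available measurement prior to the administration of investigational product". Note c to the visit-window table in SAP Section 19.1 repeats it: "Baseline visit value is defined as the last available measurement prior to BMN 270 dosing". Neither mentions an assay.

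Protocol Table 9.1.1 schedules AAV5 TAb at Screening, at Smart Rescreening if used, at Baseline, and before dosing on the infusion day. Footnote c divides these samples between two assays. On one side, "Screening, Smart Re-screening, and Infusion Day samples will be tested in an AAV5 TAb pre-screening assay specifically developed for enrollment purposes". On the other, "Baseline and all post-dose samples will be tested in a different AAV5 TAb post-dose immunogenicity monitoring assay".

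For the AAV5 tests, TI included, SAP Section 15 says they "will be tested at the Screening visit before BMN 270 infusion is given and at post-baseline visits". The text after the AAV5 sentence is redacted. In the protocol, the entry "Blood sample for AAV5 TI assay" is in Section 12.3 (Baseline Visit). The Screening list in Section 12.2 has TAb but no TI.

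On the form of reporting, SAP Section 5.2 says: "Only listings will be provided since only one subject was enrolled".

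**The concern.** A baseline is useful only if it was measured in the same way as the values set against it. The protocol arranges this for AAV5 TAb by running the Baseline-visit sample in the monitoring assay. The SAP rule goes by time alone, and the last pre-dose sample is the infusion-day one, run in the enrollment assay. If the rule were programmed across all TAb records as a single assessment, the baseline flag would pass over the one comparable sample and land on an enrollment result. A reader of the listing could then take a difference between assays for a response to the vector.

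The TI wording adds to the unease. A SAP that names a visit at which no TI sample is scheduled suggests that the section was not checked against the schedule, and a programmer searching for a Screening TI record would find none.

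**Working it through.** No sample size, power or error rate is involved. The check is to order the scheduled samples and apply the rule under each reading.

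**AAV5 TAb, pre-dose** (Protocol Table 9.1.1 with footnote c; Sections 12.2, 12.2.1, 12.3 and 12.4), in time order:

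| Sample | Assay |
|---|---|
| Screening | enrollment |
| Smart Rescreening (only if used) | enrollment |
| Baseline, Day -7 to Day -1 | monitoring |
| Infusion day, before dosing | enrollment |

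Scheduled pre-dose samples: 1 + 1 + 1 = 3, or 3 + 1 = 4 with rescreening. In either case 1 is in the monitoring assay.

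**AAV5 TAb, post-dose, Year 1** (Protocol Sections 12.5.9 and 12.6.6): Weeks 8, 16 and 24 plus Weeks 32, 36 and 52, so 3 + 3 = 6. All 6 are in the monitoring assay.

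**Applying SAP Section 5.5 to TAb.**
- TAb as one assessment: the last pre-dose record is the infusion-day enrollment result. It does not match the 6 post-dose results.
- Each assay as its own parameter: the last pre-dose monitoring record is the Baseline-visit result, which matches all 6. The enrollment results form a separate series used for eligibility.

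The second reading is the natural one. The protocol itself describes the tests as different assays with different purposes. Section 5.5 is equally silent about FVIII activity, which Protocol Sections 12.2 and 12.3 measure by both a chromogenic and a one-stage assay. Nobody would take that silence as leave to use a one-stage baseline for chromogenic results.

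**Does note c in SAP Section 19.1 strengthen the literal reading?** Its Baseline window runs up to and including Day 1, so it would admit the infusion-day sample. But the table is headed for liver tests, vital signs and other central laboratory tests. Protocol Section 6 separates central-laboratory work from bioanalytical samples sent to specialty laboratories. Nothing visible places AAV5 TAb in that table, so note c adds little.

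**TI.** Scheduled pre-dose samples: Baseline visit, 1; Screening, 0. The last pre-dose TI measurement is therefore the Baseline-visit sample, the only one there is. The Section 5.5 rule selects it without using the visit name in Section 15.

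**Where could a TAb baseline appear?** The baseline characteristics in SAP Section 9 contain no AAV5 item. No visible section derives a change in AAV5 TAb or tests one. The analysis covers one subject, by listing.

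**The case for a change.** The strongest case for a change is that the visible SAP never tells the analyst to separate the two TAb assays. Section 15 does distinguish the binding and neutralizing assays for FVIII antibodies, yet for AAV5 it speaks only of TAb and TI. The listings support a marketing application, so their labels should be right. Section 15 also plans a figure of immunogenicity and alanine transaminase over time, in which the choice of pre-dose point could show. The repair would be a few words.

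Part of this stands. The SAP is silent on assay, and the TI visit name does not match the protocol. Section 15 uses the word baseline for cellular immunity, so Screening there is not simply its term for pre-dose.

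The rest carries less weight. The figure is described directly after the cellular-immunity text and may not include TAb. Even if it does, plotting values over time needs no baseline flag. The place where an AAV5 reporting rule would most naturally sit is redacted, so the visible silence does not establish a gap. The TI label also fits the documents' loose use of screening for the whole pre-dose period. SAP Section 5.3 refers to screening visits when it explains negative study days, and Protocol Section 9.3.5 counts 4 weeks of screening, the infusion day, 52 weeks and 208 weeks (4 + 52 + 208 = 264) with no separate baseline period. For FVIII antibodies, too, Section 15 names only Screening before dosing, although Protocol Section 12.3 also samples them at Baseline.

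**Conclusion.** No change follows. The TAb point is an ambiguity that ordinary handling by parameter resolves in the direction the protocol intends. The TI point is a descriptive slip that misdirects no derivation. The most that could go wrong is a baseline label on the wrong row of a listing for one subject. No visible summary, comparison or test would move. Adding that the rule applies within assay, or correcting the visit name, would be harmless tidying with no effect on any visible result.

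This rests on three assumptions: that the two TAb assays are held as separate parameters, as their description in the protocol invites; that the redacted parts of SAP Section 15 and of the general considerations in SAP Section 5 do not introduce a TAb change from baseline across assays; and that reporting stays at listings for the single enrolled subject. If a later analysis summarized AAV5 TAb change over several subjects, the within-assay rule would be worth stating.
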